12. ADVERSE EVENTS

Throughout the course of the study, all adverse events will be monitored and reported on an adverse event CRF/eCRF without omitting any requested and known information. When AEs occur, the main concern is the safety of the study subjects. At time of the informed consent signature, each subject must be given the name and phone number of investigational site personnel for reporting AEs and medical emergencies.

At each visit, after the subject has had the opportunity to spontaneously mention any problems, the investigator should inquire about AEs by asking the standard questions:

Protocol Version 1:

This document contains confidential, proprietary information.

Protocol GLI.04.US.SL.017

CONFIDENTIAL

- “Have you had any health problems since your last study visit?”
- “Have there been any changes in the medicines you take since your last study visit?”

AEs should be reported for any clinically relevant change, as determined by the Investigator, in concomitant medication(s) that is the result of an untoward (unfavorable and unintended) change from baseline in a subject's medical health following exposure to the study treatment.

Changes from baseline in any protocol-specific parameter evaluated during the study are to be reviewed by the Investigator. In addition, the subject's responses to any questionnaire utilized during the study are to be reviewed by the investigator. Any untoward (unfavorable and unintended) change from baseline in a protocol-specific parameter or question response that is clinically relevant, in the opinion of the investigator, is to be reported as an AE. These clinically relevant changes will be reported regardless of causality.

12.1 Definitions

12.1.1. Adverse Events (AE)

An adverse event (AE) is defined as any untoward medical occurrence in a subject taking part in the clinical study, and which does not necessarily require a causal relationship with the investigational product and/or a clinical trial procedure.

An AE can be any unfavourable and unintended sign (including an abnormal laboratory value), symptom, or disease temporally associated with the use of the investigational product, whether or not related to this product.

When an AE has a likely or very likely causal relationship with the investigational product and/or a clinical trial procedure, it is named undesirable effect or related AE (see Section 3).

12.1.2. Local tolerability signs and symptoms (only applicable for cosmetic safety studies)

In cosmetic studies, local skin tolerability includes some expected functional and/or physical signs on the application area, observed by the Investigator or reported by the subjects (see Appendix). Those signs are collected in the final report based on scales or a diary. If the severity of a local skin tolerability sign or symptom, is such that the product application is permanently discontinued and/or a corrective concomitant treatment (except moisturizer or emollient) is prescribed, it is recorded as an undesirable effect (related AE).

12.1.3. Serious Adverse Events (SAE) and serious undesirable effect/related SAE

A Serious Adverse Event (SAE) is any adverse event which results in death, is life-threatening, requires inpatient hospitalization or prolongation of existing hospitalization, results in persistent or significant disability/incapacity, or is a congenital anomaly/birth defect.

Notes:

The term “immediate vital risk” refers to an event in which the subject was at risk of death at the time of the event; it does not refer to an event that hypothetically might have caused death if it was more severe.

Protocol Version 1:

This document contains confidential, proprietary information.

Protocol GLI.04.US.SL.017

CONFIDENTIAL

Inpatient hospitalization is considered to have occurred if the subject has had to stay for a night at the hospital. Hospitalization solely for the purpose of a diagnostic test (even if related to an AE), elective hospitalization for an intervention that was already planned before subject enrolment in the clinical trial, admission to a day-care facility, social admission (e.g., if the subject has no place to sleep), or administrative admission (e.g., for a yearly examination) should not be considered as a SAE.

A serious undesirable effect/related SAE is defined as any SAE which the Investigator classifies as having a reasonable possibility for a causal relationship with the investigational product and/or the clinical trial procedure.

12.2 Severity Assessment

For all AEs occurring during the clinical trial, the Investigator is to classify and report the intensity of AEs using the following definitions as a guideline:

- Mild: awareness of signs and symptoms, but easily tolerated
- Moderate: discomfort, enough to cause interference with usual activity
- Severe: incapacitating, with inability to work or perform usual activity.

12.3 Causality Assessment

The Investigator is to assess the causal relationship (causality) between an adverse event and the investigational product and/or the clinical trial procedure according to the following definitions (Decision of 25 November 2013 on Guideline on Annex I to Regulation (EC) No 1223/2009 (2013/674/EU) - Causality assessment of undesirable effect caused by cosmetic products):

- Very likely
- Likely
- Not clearly attributable
- Unlikely
- Excluded

Medical judgment should be used to determine the relationship, considering all relevant factors including the pattern of reaction, temporal relationships, positive de-challenge or re-challenge, relevant medical history, and confounding factors such as co-medication or concurrent diseases.

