9.1.2. Visit 2 (Baseline/Day 0 – Surgical procedure)

1. Investigator or clinic staff will ask the subjects if they have experienced any changes in their health since the previous visit.
2. Before the surgical procedure, the assessments below will be completed:
 - a. Clinical grading by Investigator as described in section 10.1
 - b. Tolerability assessment by the subjects as described in section.
3. The surgical area will be assessed and prepped for the procedures, followed by procedure execution by Investigator.
4. After the surgical procedure, the assessments below will be completed:
 - a. Standardized photography as described in section 10.3
 - b. Clinical grading by Investigator as described in section 10.1
 - c. Tolerability assessment by the subjects as described in section 10.2
5. Investigator or clinic staff will apply the treatment product to the surgical site followed by standard bandage.
6. Subjects will be given the treatment product with instruction of application, a diary to record usage of the treatment product, and when to contact the Investigator in case of emerging AEs.
7. Subjects will be scheduled for a follow-up visit at Day 7 or 14 (± 2 days) and dismissed from the Clinic.

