12.4.1. Management and reporting procedures for undesirable effects (i.e. related adverse events)

Undesirable effects should be recorded in the CRF and summarized in the report in a summary table with at minimum the subject number, AE number, AE diagnosis or signs and symptoms, location, date of onset, seriousness, severity, action taken, relationship, date of resolution and concomitant treatment associated as well as a detailed narrative of the event.

In addition, based on his/her medical judgment, the Investigator will assess whether an undesirable effect requires immediate (i.e. within 24 hours) reporting to the Sponsor. In such cases, the summary table will be sent to the Sponsor, along with the AE narrative and any other relevant information (concomitant treatments, product weighing, ...).

All undesirable effects should be appropriately documented, i.e. any relevant information such as demographics, medical history and concomitant therapies should be recorded in the CRF.

The Investigator is to monitor and record the progress of the adverse effect until the last subject's study visit.

The Investigator is to update the AE narrative as appropriate, each time follow-up information is collected and when the final outcome of the adverse effect is known.

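### Causality is judged jointly against ointment and/or trial procedure, and the status of the surgery is undefined, so the related-AE count can mix surgical and ointment events

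*Combined protocol and SAP*

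**What the plan says.** Section 12.3 instructs the investigator to "assess the causal relationship (causality) between an adverse event and the investigational product and/or the clinical trial procedure", using one scale that runs from very likely to excluded.

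The definitions follow the same joint target:
- Section 12.1.1, for AEs: "When an AE has a likely or very likely causal relationship with the investigational product and/or a clinical trial procedure, it is named undesirable effect". The section uses this label interchangeably with related AE.
- Section 12.1.3, for SAEs: a related SAE is one with a "reasonable possibility for a causal relationship with the investigational product and/or the clinical trial procedure".

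Section 12.1.2 is headed as applying only to cosmetic safety studies. It states that "local skin tolerability includes some expected functional and/or physical signs on the application area" and has these signs collected by scales or diary. That changes when a sign is severe enough that application is stopped for good and/or "a corrective concomitant treatment (except moisturizer or emollient) is prescribed, it is recorded as an undesirable effect (related AE").

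Section 12.4.1 asks for a summary table of undesirable effects whose minimum content includes "seriousness, severity, action taken, relationship, date of resolution", together with a detailed narrative of each event. Section 12.4 sets the minimum to be reported as related AEs plus all SAEs.

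The surgery itself is a numbered step of Visit 2 in Section 9.1.2: the area is prepared, "followed by procedure execution by Investigator".

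**The concern.** Section 5.1 makes the safety of the ointment an objective. All subjects have a Mohs procedure, biopsy or excision on the day they start the ointment, and the two act on the same skin. An AE at the site can come from either. The definition of *related* accepts either cause and does not ask which one it was.

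Two things could go wrong. Events caused only by surgery could raise the related-AE count and make the ointment look worse than it is. A genuine ointment reaction could also be one line among several surgical ones and be discounted. Because the study is multi-center and *clinical trial procedure* is undefined, the same event could be related at one site and unrelated at another. For non-serious events, that label can also decide whether the event appears in the report at all, given the minimum set in Section 12.4.

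**Working it through.** The documents state no AE rate and Section 11 plans no AE summary, so there is no figure of the plan's to reproduce. The check is mainly textual.

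**1. Is the surgery a clinical trial procedure?** The term is not defined, and the text points both ways.
- Against: inclusion criterion 2 (Section 6.3) requires a diagnosis that itself calls for the procedure, which suggests ordinary care.
- For: the surgery is in the Section 9 visit list and flow chart, the investigator performs it under Section 9.1.2, and its risks are explained to subjects at screening (Section 9.1.1). The other scheduled activities are grading, photography, questionnaires and diaries, which are unlikely causes of an AE.

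Both readings are reasonable.

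**2. What follows under each reading?** If the surgery counts, an AE judged likely due to surgery alone meets the Section 12.1.1 definition and goes in the Section 12.4.1 table. If it does not count, the same AE stays out.

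**3. Does Section 12.1.2 separate the causes?** Below its threshold, expected local signs stay in the scales or diary. Above it, the sign is recorded as related without any judgement under Section 12.3. Pain at the surgical site is a graded tolerability item (Section 10.2), so surgical pain severe enough to lead to a corrective prescription could take this route. Whether the section applies is itself unclear: Section 4 and Appendix I describe an OTC skin protectant with a listed active ingredient. The section also refers to an appendix for the expected signs, but Appendix I lists ingredients and Appendix II is the questionnaire.

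**4. How much could it matter?** This is an illustration with assumed rates. Let *s* be the share of subjects with a surgery-caused AE that is reported and rated likely or very likely, and *o* the share with an ointment-caused AE, independent of each other. Take n = 20 (the completers in Section 6.1).
- Share of subjects in the table = 1 − (1 − s)(1 − o).
- Inert ointment (o = 0): expected subjects = 20s; chance of at least one = 1 − (1 − s)^20.
- With o = 5%: share of listed subjects who had an ointment-caused event = 0.05 / [1 − (1 − s)(0.95)].

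| s (assumed) | Expected in table, o = 0 | Chance of at least one, o = 0 | Share in table, o = 5% | Of those, with ointment event |
|---|---|---|---|---|
| 5% | 1 | 64% | 9.75% | 51% |
| 10% | 2 | 88% | 14.5% | 34% |
| 20% | 4 | 99% | 24.0% | 21% |
| 30% | 6 | 99.9% | 33.5% | 15% |

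For the inert ointment, an ointment-only count would be 0/20, with an exact two-sided 95% upper limit of 1 − 0.025^(1/20) = 16.8%.

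The effect of the definition alone can be shown with assumed counts. Four subjects with a surgical AE and one other with an ointment reaction give 5/20 = 25% if surgery counts and 1/20 = 5% if it does not.

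**The case against.** A reader might infer that the expected effects of surgery generally count as undesirable effects. The documents do not support that. Section 12.1.2 keeps expected local signs in the scales or diary unless its threshold is passed, and Section 12 limits AEs arising from study parameters to untoward, unintended changes that the investigator finds clinically relevant. Ordinary post-operative swelling or soreness is not listed by default. Nor must a site rate post-operative events as very likely related, because Section 12.3 calls for medical judgement on all relevant factors.

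A reader might also infer that ointment safety cannot be read at all. That is too strong. Section 12.4.1 requires a narrative and several descriptors for every undesirable effect, and with 20 completers the listing would probably be short enough to read event by event. Section 12.6 adds a product-specific test for suspected allergy, with patch re-challenge and possible ingredient testing.

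Finally, a single rating is inferred from the *and/or* wording and the one relationship item. The table content is stated as a minimum, the AE form is not among the documents, and the form may already hold two fields.

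These points narrow the concern but do not remove it. Nothing requires the narrative or the relationship entry to name the cause, re-challenge covers only suspected allergy, and Section 12.1.2 assigns relatedness without attribution exactly where events are more severe.

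**Conclusion.** The point holds in limited form. The plan does not require separate attribution to ointment and surgery and leaves *clinical trial procedure* undefined, so the related-AE count can mix the two sources and can differ by site. Ointment safety cannot be reliably read from that count alone.

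The effect depends on sites treating the surgery as a trial procedure, or on Section 12.1.2 applying and its threshold being passed. The 1 to 6 of 20 subjects in the illustration rests on assumed rates of 5% to 30% and is not a forecast. The plan computes no AE rate, and the 25% versus 5% contrast shows only how far the definition could move a count. Tolerability scores and expected signs below the threshold are outside this point. It is worth correcting because safety is an objective and the change is cheap.

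**What to change.** - **Section 12.3:** state whether the Visit 2 surgery is a clinical trial procedure, and have the investigator rate causality separately for the ointment and for the surgical procedure on the existing five-level scale.
- **Section 12.4.1:** show both ratings as separate columns, and give the ointment-related count on its own.
- **Section 12.4:** say explicitly that procedure-related events stay in the minimum reporting set, so that non-serious ones are not lost when the ratings are split.
- **Section 12.1.2:** say whether it applies to this study. If it does, keep the recording trigger but add both ratings, so that the automatic related label does not by itself count as ointment-related.

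The cost is one CRF field, if the form now has a single causality entry, plus one table column and some wording. Some events will be not clearly attributable to either cause. With no control arm, the split remains investigator judgement; the change makes that judgement visible and consistent across sites.

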12.4 Collection, Management and Reporting Procedures

The period of collection of adverse events starts from the time of signature of the Informed Consent Form (ICF) by the subject (*and/or, for subjects who are minor, by the parents/legal representatives*) until the end of the subject's participation in the clinical study.

If a Serious Adverse Event (SAE) is on-going at the final clinical trial visit, it should be followed by the Investigator until it has resolved or has reached a stable condition.

After the subject completes the clinical study, the Investigator should also inform the Sponsor (see Sponsor's contact details below) if he/she becomes aware of an SAE involving a subject who has participated in the clinical study.

At each post-enrollment visit, the Investigator will question the subject about AEs using an open non-persuasive question to elicit reporting of AEs, for example "*Have you noticed any change in your health since the last visit?*" Direct questioning and examination will be performed when appropriate.

Protocol Version 1:

This document contains confidential, proprietary information.

Protocol GLI.04.US.SL.017

CONFIDENTIAL

The Investigator will obtain and maintain in the subject's files all pertinent medical records, and (if applicable) information and medical judgment from colleagues who assisted in the treatment and follow-up of the subject. If necessary, the Investigator will contact the subject's personal physician or hospital staff to obtain further details.

As a minimum, Investigators are requested to report in the Case Report Form (CRF) and in the report all related adverse events (i.e. undesirable effects) and all Serious Adverse Events, whether related or not.

12.4.1. Management and reporting procedures for undesirable effects (i.e. related adverse events)

Undesirable effects should be recorded in the CRF and summarized in the report in a summary table with at minimum the subject number, AE number, AE diagnosis or signs and symptoms, location, date of onset, seriousness, severity, action taken, relationship, date of resolution and concomitant treatment associated as well as a detailed narrative of the event.

In addition, based on his/her medical judgment, the Investigator will assess whether an undesirable effect requires immediate (i.e. within 24 hours) reporting to the Sponsor. In such cases, the summary table will be sent to the Sponsor, along with the AE narrative and any other relevant information (concomitant treatments, product weighing, ...).

All undesirable effects should be appropriately documented, i.e. any relevant information such as demographics, medical history and concomitant therapies should be recorded in the CRF.

The Investigator is to monitor and record the progress of the adverse effect until the last subject's study visit.

The Investigator is to update the AE narrative as appropriate, each time follow-up information is collected and when the final outcome of the adverse effect is known.

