12.4.2. Management and reporting procedures for Serious Adverse Events

The Investigator is to take the following steps:

1. Take prompt and appropriate medical action, if necessary. The safety of clinical trial subjects is the first priority
2. Ensure the AE is classified as an SAE. Immediately inform the Sponsor's representative of the event by email or fax (see contact details below) and discuss further actions to be taken:

e-mail: [contact]

3. Complete the Serious Adverse Event (SAE) form provided by the Sponsor's representative **Within 24 hours**, fax or send by e-mail **to the Sponsor's representative** the completed SAE form, accompanied any other relevant information (e.g. test results or medical records).
4. Monitor, record and send to Sponsor's representative the progress of the event until it resolves or reaches a stable outcome, with or without sequelae (send the updated SAE form with follow-up information and any other relevant information to Sponsor's representative).
5. Obtain and maintain in the subject's file all pertinent medical records, information, and medical judgments from colleagues who assisted in the treatment and follow-up of the

Protocol Version 1:

This document contains confidential, proprietary information.

Protocol GLI.04.US.SL.017

CONFIDENTIAL

subject. If necessary, contact the subject's personal physician or hospital staff to obtain further details.

6. If applicable, comply with the regulatory requirement(s) related to the reporting of SAEs to the Institutional Review Board (IRB) / Independent Ethics Committee (IEC).

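### Section 12.4.1 stops follow-up of non-serious product-related effects at the last visit, yet asks for a resolution date and a final outcome

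*Combined protocol and SAP*

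**What the plan says.** Section 12.4.1 covers related adverse events, which the protocol calls undesirable effects. It sets the end of follow-up: "The Investigator is to monitor and record the progress of the adverse effect until the last subject's study visit". The report's summary table must include "severity, action taken, relationship, date of resolution and concomitant treatment associated". The narrative is to be updated "each time follow-up information is collected and when the final outcome of the adverse effect is known".

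The rule for serious events is different. Under section 12.4, for an SAE still ongoing at the final visit, "it should be followed by the Investigator until it has resolved or has reached a stable condition". Step 4 of section 12.4.2 repeats this: "Monitor, record and send to Sponsor's representative the progress of the event until it resolves or reaches a stable outcome".

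Suspected allergic reactions have their own procedure in section 12.6: stop the product, wait for all signs to clear, patch re-challenge with three readings, a sensitization rating, and a report to the sponsor. The last scheduled visit is Visit 4, Day 28 ± 3 days (section 9.1.4).

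**The concern.** The stop rule and the items the section requires do not fit together. An effect still open when monitoring ends has no resolution date and no final outcome, and nothing obliges anyone to find them out later. The narrative rule does not close this: it applies when information is collected or the outcome becomes known, and does not require the investigator to seek either.

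Safety is half of the stated objective (section 5.1), and the effects concerned are those attributed to the product. Some may have needed action. Section 12.1.2 says of a local sign or symptom that if it is severe enough that "the product application is permanently discontinued and/or a corrective concomitant treatment (except moisturizer or emollient) is prescribed, it is recorded as an undesirable effect". That section's heading limits it to cosmetic safety studies, so its application here is not certain, but it shows that the non-serious class is not confined to trivial events. At stake is the completeness of the safety record: how long such an effect lasted and how it ended.

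**Working it through.** The protocol states no figure to reproduce. The check is to set the follow-up rules side by side and see which events remain uncovered.

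| Event | Section | Active follow-up ends |
|---|---|---|
| Serious adverse event | 12.4; 12.4.2 step 4 | Resolved or stable |
| Suspected allergic reaction | 12.6 | Last patch reading, with resolution required before re-challenge starts |
| Other non-serious related effect | 12.4.1 | Last subject's study visit |

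**Does section 12.6 really run past the visit?** The inputs are at least 14 days from the last application (step 1), 48 hours of occlusion = 2 days (step 4), and a third reading 72 or 96 hours after removal = 3 or 4 days (step 6).

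- Shortest first re-challenge: 14 + 2 + 3 = 19 days, or 14 + 2 + 4 = 20 days, after the last application.
- With Visit 4 on Day 28, the last reading falls after the visit if the product is stopped after Day 9 (28 − 19) or Day 8 (28 − 20).
- At the edges of the visit window the cut-offs are Day 6 or 5 (25 − 19, 25 − 20) and Day 12 or 11 (31 − 19, 31 − 20).
- A positive, equivocal or irritant result normally leads to a further patch series after at least two more weeks. If these are counted from the end of the first round, the minimum total is 2 × 19 = 38 to 2 × 20 = 40 days, past Day 31 for any stop day.

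Section 12.6 sets no limit at Visit 4, and its own timetable often cannot finish by then. Allergic reactions are therefore carried forward. This arithmetic shows that they lie outside the gap; it does not measure the gap.

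**What the two readings of the stop phrase give.** If it means the subject's own last visit, monitoring after Visit 4 lasts 0 days for everyone. If it means the trial's last visit, a subject whose Visit 4 falls k days before the last subject's has k more days, and the last subject has k = 0. The documents give no recruitment period, so k is unknown. The second reading shrinks the gap but does not remove it for late enrolees.

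**What remains.** The third row of the table: non-allergic, non-serious effects attributed to the product and still open at the stop date. The documents give neither the frequency nor the duration of such effects, so no count can be derived.

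**Effect on the analysis.** Section 11 tests change from pre-procedure baseline in clinical grading and tolerability scores at the scheduled time points and tabulates the questionnaire. None of these uses data collected after Visit 4.

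**The case against.** The strongest reply is that time-limited follow-up is proportionate. The trial has 20 completers using a petrolatum ointment, serious events are followed fully, and an effect open at Day 28 can be listed as ongoing. Section 14.2 allows later adverse event additions to the CRF, and the narrative must be updated if an outcome becomes known. All of this stands, and it is why the point is minor. It does not supply active follow-up, because each of these provisions handles information that has already arrived.

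A second objection concerns the fix. Sections 12.1.1 and 12.3 use one causality judgment for the product and/or the procedure, and redness or itching at a fresh surgical wound may be hard to assign. That also stands, and it is counted as a cost below.

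A reader might go further and infer that a re-challenge result arriving after Day 28 is lost, or that causality may be left unrevised. The documents do not support this. Section 12.3 names "positive de-challenge or re-challenge" among the factors to weigh and sets no cut-off date. Section 12.6 requires the result to be rated and reported to the sponsor. Sections 12.4.1 and 14.2 leave room for later updates. What is absent is only an explicit step linking the sensitization rating in 12.6 to the five-level causality rating in 12.3. Since 12.1.1 gives the related label "When an AE has a likely or very likely causal relationship with the investigational product and/or a clinical trial procedure", such a line would be tidy, but its absence is missing detail, not an error.

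**Conclusion.** The point holds in a narrow form. Section 12.4.1 states a stop rule that does not fit the items it requires, and it leaves non-serious, non-allergic product-related effects that are open at the last visit without required active follow-up. Severity is minor. The size of the gap cannot be estimated from the documents; any figure would rest wholly on assumed rates and durations. The conclusion does not depend on which reading of the stop phrase is intended, though the trial-wide reading makes the gap smaller. It should not be read as a failure to follow serious events or suspected allergic reactions, or as a threat to any endpoint or test.

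**What to change.** In section 12.4.1, for undesirable effects for which the investigator considers the study product a likely or very likely cause, replace the stop phrase with: *until the effect has resolved or is stable*. For effects attributed only to the procedure, state that monitoring ends at the subject's own last visit. This also settles the ambiguous phrase and avoids open-ended follow-up of ordinary surgical after-effects.

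The cost is an occasional contact after Day 28, a possible late addendum to the report, and an entry noting whether relatedness is to the product or the procedure, which the present single rating does not separate.

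Optional wording: add to 12.6 that the 12.3 causality rating is revisited after the last reading of the first re-challenge. Tying it to the first round keeps this step from waiting on a later patch series, which may start up to 6 months afterwards.
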